5.3.4. Other Lifestyle Requirements

- Participants should not apply occlusive dressing(s) to the areas treated with IP.
- Participants should not swim, bathe, be bathed or have treatment areas washed for at least 4 hours after application of the IP.
- Use of sunscreen and regular moisturizers is permitted, but only on areas which are not treated with IP.
- The participant should avoid wiping the IP off the skin and the IP should not be re-applied to areas that were inadvertently wiped until the next scheduled dose.
- Participants will agree to avoid strenuous exercise during the study, especially within 48 hours prior to the scheduled study visits and maintain adequate hydration, if possible.

- On study visit days, the participants will not smoke or use nicotine-containing products, or ingest caffeine (eg, tea, coffee, some soft drinks/colas/energy drinks and power bars) during the 2 hours prior to blood pressure and pulse (heart) rate measurements.
- On study visit days, showering or bathing is permitted prior to attending the study visit, but moisturizing will not be done.
- On study visit days, prescribed permitted concomitant medication will be taken, as needed, prior to the study visit, if it can be administered with water only.
- The participants will contact the study site investigator if there are any changes or additions to concomitant medications.
- The participants will avoid having major elective surgery until after the final study assessments.
- The participants should continue all non-pharmacological therapies, such as physical therapy, as indicated. However, the participants should avoid changing the type or intensity of therapy or initiating new therapy until after Week 6 visit.
- When applying the IP, the participant will not be required to wear gloves. However, participants should be instructed to wash their hands with mild soap and water before and after each application.
- If study participants need someone else to assist with applying investigational product on hard to reach areas (eg back), this person must wear gloves to avoid accidental exposure to the IP.

5.4. Screen Failures

Screen failures are defined as participants who consent to participate in the clinical study but are not subsequently randomly assigned to study intervention. A minimal set of screen failure information is required to ensure transparent reporting of screen failure participants to meet the CONSORT publishing requirements and to respond to queries from regulatory authorities. Minimal information includes demography, screen failure details, eligibility criteria, and any SAE.

Individuals who do not meet the criteria for participation in this study (screen failure) may be re-screened **once** if they fail the screening evaluation for reasons related to incidental transitory conditions, unless the reason for the screen failure is the disease severity inclusion criteria. Participants may not be rescreened unless approved by the sponsor. Rescreened participants should be assigned a new participant number.

6. STUDY INTERVENTION

Study intervention is defined as any investigational intervention(s), marketed product(s), placebo, medical device(s), or study procedure(s) intended to be administered to a study participant according to the study protocol.

For the purposes of this protocol, study intervention refers to PF-07038124 0.01% ointment and PF-07038124 vehicle ointment (placebo).

6.1. Study Intervention Administered

Intervention Name	PF-07038124 0.01% ointment	PF-07038124 vehicle ointment
ARM Name (group of patients receiving a specific treatment (or no treatment))	Participants with mild or moderate AD, or mild or moderate psoriasis	Participants with mild or moderate AD, or mild or moderate psoriasis
Type	Drug	Drug
Dose Formulation	Ointment	Ointment
Unit Dose Strength(s)	0.1 mg/g ointment in 60-gram tube	0 mg/g ointment in 60-gram tube
Dosage Level(s)	0.01% (wt/wt), QD	0% (wt/wt), QD
Route of Administration	Topical	Topical
Use	Experimental	Placebo
IMP or NIMP	IMP	IMP
Sourcing	Provided centrally by the sponsor.	Provided centrally by the sponsor.
Packaging and Labeling	Study intervention will be provided in cartons. Each carton will contain one tube. Both the carton and tube will be labeled in a blinded format as required per country requirement.	Study intervention will be provided in cartons. Each carton will contain one tube. Both the carton and tube will be labeled in a blinded format as required per country requirement.

CCI

6.1.1. Administration

6.1.1.1. Treatable Areas

AD treatable areas will be all areas affected by AD, except scalp.

Psoriasis treatable areas will be all areas affected by psoriasis, except scalp and nails.

A thin layer of IP ointment will be applied at a target application rate of approximately 3 mg/cm² by using a fingertip unit (FTU) method.

Day 1 Visit

At the Day 1 Visit, before the Day 1 initial IP application is performed, the designated areas for treatment will be identified and documented in the participant's source document study records (body map). The participant and/or caregiver will be provided with a paper version of the body map.

On Day 1 through the final dose at Week 6 visit, the IP should be applied once daily (around same time of the day), to all treatable AD or psoriasis involved areas identified at the Day 1 visit.

All participants will be supplied with instructions on application and dose frequency commensurate to assigned treatment arm. Those participants having difficulty reaching treatment-eligible areas (eg, back) may be assisted by another person who will need to apply the IP to the participant according to the investigational product application instructions. The person assisting with the application must wear gloves to avoid any exposure to the IP.

Participants and/or caregivers will be encouraged to observe and participate in the initial IP application on Day 1.

Post Day 1 Visits

After Day 1/Randomization, all subsequent doses will be applied at home except the dose on the days of in-clinic visits. CCI

The last dose of IP will be applied during the Week 6 in-clinic visit (EOT visit) as specified in [Section 1.3.3](#) of the [SoA](#).

The participant and/or caregiver will be instructed to complete the Dosing Diary starting with the first dose applied in the clinic on Day 1 through Week 6 (each time IP is applied) for all IP doses applied. If a participant misses applying a dose, the participant should apply this dose provided this dose should have been applied within the last 6 hours. For longer intervals, the dose should be skipped. The missed dose should be recorded in the dosing diary. The next dose should be applied according to the regular dosing regimen.

Treated area identified on Day 1 should be continued to be treated even if substantial improvement or clearing of AD or psoriasis occurs. The reason for maintaining IP treatment areas the same as identified at Day 1 is to understand the efficacy, systemic safety, and local tolerability of PF-07038124 ointment when applied to for 6 weeks in participants with mild or moderate AD or psoriasis.

Post Day 1, any new AD or psoriasis on treatment-eligible areas identified by the participant or caregiver(s) should also be treated with the IP. Decision to apply the IP to new eligible areas should be made following assessment by the Investigator or his/her designee. An unscheduled visit for assessment of the new lesion may be required at the discretion of the investigator. Body map will be updated, and IP need will be re-assessed at every site visit during the treatment period. If the total, treatable BSA exceeds 20% (AD) or 15% (psoriasis) during the six-week treatment period, the participant will still remain eligible for the study, given that the total, treatable BSA does not exceed 22% (for AD) or 16.5% (for psoriasis). If the total, treatable BSA exceeds 22% (AD) or 16.5% (psoriasis), the Sponsor may decide to discontinue the participant.

Participants and/or caregivers will be instructed not to wipe investigational product off the skin, avoid applying an occlusive dressing to the treated areas, and refrain from swimming or bathing/washing the treated areas within 4 hours after application.

Under no circumstances will the investigational drug application regimen be modified (eg, frequency of application increased or reduced, not stopped, or the application rate [target 3 mg/cm²] increased or reduced) during the study. Temporary discontinuation of investigational drug may be appropriate under some circumstances (eg, surgery, non-serious infections) and should be discussed with the Medical Monitor (or designee) preferably prior to temporary discontinuation of investigational drug.

Study intervention administration details will be recorded on the CRF.

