1.3.1. Atopic Dermatitis

ATOPIC DERMATITIS								
Visit Identifier ^a	Screening & Washout	Day 1 (Baseline)	Week 1	Week 2	Week 4	Week 6 (EOT)	Follow-up (EOS)	Early Termination (ET)
Visit Window	Day-42 to -1	N/A	Day 8 ±2	Day 15 ±2	Day 29 ±2	Day 43 ±2	28–35 Days post-last Dose	N/A
Visit Number	1	2	3	4	5	6	7	N/A
Enrollment Procedures								
Informed Consent	X							
Register Subject Using IRT System	X							
Medical History	X	X						
Concomitant/Prior Treatments	X	X	X	X	X	X	X	X
Demography	X							
Eligibility Assessment	X	X						
Randomization		X						
Clinical Assessments								
Complete Physical Examination ^b	X	X				X		
Targeted Physical Examination ^b			X	X	X		X	X
Weight	X	X						
Height	X							
Vital Signs ^c	X	X		X	X	X		X
ECG ^d	X	X				X		
C-SSRS ^e	X							
Laboratory Assessments								
Serum FSH (WONCBP only) or Serum Pregnancy Test (WOCBP only) ^f	X							

ATOPIC DERMATITIS

Visit Identifier ^a	Screening & Washout	Day 1 (Baseline)	Week 1	Week 2	Week 4	Week 6 (EOT)	Follow-up (EOS)	Early Termination (ET)
Visit Window	Day-42 to -1	N/A	Day 8 ±2	Day 15 ±2	Day 29 ±2	Day 43 ±2	28-35 Days post-last Dose	N/A
Visit Number	1	2	3	4	5	6	7	N/A
Urine Pregnancy Test (conducted at study site) ^g		X	X	X	X	X	X	X
Hematology, Chemistry and Urinalysis ^h	X	X	X	X	X	X	X	X
Fibrinogen, hsCRP ^h	X	X	X	X	X	X	X	X

IP Related Processes								
Dispense dosing diary/PROs and instruct on usage	X							
Assess BSA & calculate IP need	X	X	X	X	X			
Body Map		X	X	X	X	X		
Weigh and dispense IP		X	X	X	X			
IP application and observation (at site/at home in case of Home Health Visits)		X	X	X	X	X		
Record dose and time of IP application in dosing diary		X	→	→	→	X		
Collect and weigh returned IP tubes for compliance check			X	X	X	X		X
Review of dosing diary/PROs		X	X	X	X	X	X	X
Collect dosing diary/PROs		X ^k					X	X
AD-Related Clinical Assessments								
EASI	X	X	X	X	X	X	X	X
IGA	X	X	X	X	X	X	X	X

ATOPIC DERMATITIS

Visit Identifier ^a	Screening & Washout	Day 1 (Baseline)	Week 1	Week 2	Week 4	Week 6 (EOT)	Follow-up (EOS)	Early Termination (ET)
Visit Window	Day-42 to -1	N/A	Day 8 ±2	Day 15 ±2	Day 29 ±2	Day 43 ±2	28–35 Days post-last Dose	N/A
Visit Number	1	2	3	4	5	6	7	N/A
BSA	X	X	X	X	X	X	X	X
Safety Monitoring								
Contraception check	X	X	X	X	X	X	X	X
Local Tolerability Assessments ^l		X	X	X	X	X	X	X
Serious and non-serious AE monitoring	X	→	→	→	→	→	X	X
Patient Reported Outcomes (PRO)								
In-clinic completion								
At-home completion								
PP-NRS ^m	X	→	→	X	X	X	X	X

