7. DISCONTINUATION OF STUDY INTERVENTION AND PARTICIPANT DISCONTINUATION/WITHDRAWAL

7.1. Discontinuation of Study Intervention

In rare instances, it may be necessary for a participant to permanently discontinue study intervention (definitive discontinuation). Reasons for definitive discontinuation of study intervention include the following: Liver injury, ECG changes, pregnancy, local tolerability, and AEs.

Note that discontinuation of study intervention does not represent withdrawal from the study. If study intervention is definitively discontinued, the participant will proceed to ET and remain in the study to be evaluated for follow up visits. See the [SoA](#) for data to be collected at the time of discontinuation of study intervention and follow-up for any further evaluations that need to be completed. The site will inform the Sponsor Medical Monitor or Sponsor clinician if the below criteria for permanent discontinuation of the study intervention are triggered.

In the event of discontinuation of study intervention, it must be documented on the appropriate CRF/in the medical records whether the participant is discontinuing further receipt of study intervention or also from study procedures, posttreatment study follow-up, and/or future collection of additional information.

Liver Injury

Please refer to [Section 10.6 Appendix 6](#) for Potential Cases of Drug-Induced Liver Injury (DILI; Hy's law).

ECG Changes

A participant who meets either bulleted criterion based on the average of triplicate ECG readings will be withdrawn from the study intervention.

- QTcF >500 msec.
- Change from baseline: QTcF >60 msec.

If a clinically significant finding is identified (including, but not limited to, changes from baseline in QTcF after enrollment), the investigator or qualified designee will determine if the participant can continue in the study and if any change in participant management is needed. This review of the ECG printed at the time of collection must be documented. Any new clinically relevant finding should be reported as an AE.

Pregnancy

Pregnancy confirmed by serum β -hCG testing. Sponsor Clinician or Sponsor Medical Monitor should be notified immediately.

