Two negative pregnancy tests are required before randomization (1 negative serum pregnancy test at screening and 1 negative urine pregnancy test at Day 1 visit). If urine pregnancy test is positive after study intervention application, serum pregnancy test will be conducted, study intervention application paused and sponsor clinician and sponsor medical monitor notified immediately.

Local Tolerability

If a participant experiences severity Grade 3 (severe) or 4 (very severe) on the local tolerability assessment ([Section 8.2.7](#)), study treatment will be discontinued permanently, and participant will proceed to ET visit and follow-up as described in [SoA](#).

If a participant experiences application site reaction of Grade 2 (moderate) on the local tolerability assessment, investigator may temporarily discontinue application of IP for up to 48 hours without consulting the Sponsor. If in the clinical judgment of the investigator IP interruption beyond 48 hours is advisable, the investigator must obtain agreement from the Pfizer medical monitor to continue withholding IP. If temporary IP interruption for more than 5 consecutive days is needed, then the participant should be permanently withdrawn from treatment and should follow-up with the site until complete or near complete resolution of the AE. This dosing gap may occur only once for the same participant.

AEs

Hypersensitivity Reactions: If signs and symptoms of hypersensitivity are attributable to the investigational product, including contact urticaria, it must be discontinued immediately, and appropriate therapy initiated.

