7.2. Participant Discontinuation/Withdrawal from the Study

A participant may withdraw from the study at any time at his/her own request. Reasons for discontinuation from the study include the following:

- Refused further follow-up;
- Lost to follow-up;
- Death;
- Study terminated by sponsor.

At the time of discontinuing from the study, if possible, an early discontinuation visit should be conducted. See the [SoA](#) for assessments to be collected at the time of study discontinuation and follow-up and for any further evaluations that need to be completed.

The early discontinuation visit applies only to participants who are enrolled/randomized and then are prematurely withdrawn from the study. Participants should be questioned regarding their reason for withdrawal. The participant will be permanently discontinued both from the study intervention and from the study at that time.

If a participant withdraws from the study, he/she may request destruction of any remaining samples taken and not tested, and the investigator must document any such requests in the site study records and notify the sponsor accordingly.

If the participant withdraws from the study and also withdraws consent (see [Section 7.2.1](#)) for disclosure of future information, no further evaluations should be performed and no additional data should be collected. The sponsor may retain and continue to use any data collected before such withdrawal of consent.

Lack of completion of all or any of the withdrawal/early termination procedures will not be viewed as protocol deviations so long as the participant's safety was preserved.

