7.2.1. Withdrawal of Consent

Participants who request to discontinue receipt of study intervention will remain in the study and must continue to be followed for protocol-specified follow-up procedures. The only exception to this is when a participant specifically withdraws consent for any further contact with him or her or persons previously authorized by the participant to provide this information. Participants should notify the investigator in writing of the decision to withdraw consent from future follow-up, whenever possible. The withdrawal of consent should be explained in detail in the medical records by the investigator, as to whether the withdrawal is only from further receipt of study intervention or also from study procedures and/or posttreatment study follow-up, and entered on the appropriate CRF page. In the event that vital status (whether the participant is alive or dead) is being measured, publicly available information should be used to determine vital status only as appropriately directed in accordance with local law.

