8.4. Treatment of Overdose

For this study, any dose of study intervention greater than one dose within a 12-hour time period will be considered an overdose.

The maximum surface area of administration is 22% BSA for AD and 16.5% for psoriasis participants. Investigators should be aware that administration to significantly greater area may also be treated as an overdose at Investigator discretion.

The Sponsor does not recommend specific treatment for an overdose.

In the event of an overdose, the investigator should:

1. Contact the medical monitor within 24 hours.
2. Closely monitor the participant for any AEs/SAEs and laboratory abnormalities for at least 28 calendar days after the overdose of study intervention.
3. Document the quantity of the excess dose as well as the duration of the overdose in the CRF.
4. Overdose is reportable to Safety **only when associated with an SAE.**

CCI

Decisions regarding dose interruptions or modifications will be made by the investigator in consultation with the medical monitor based on the clinical evaluation of the participant.

CCI

CCI

CCI

CCI

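### Section 7.1 does not keep the scheduled Week 6 visit for participants who stop IP; the BSA-cap rule is one trigger, and it does not say what is discontinued

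*Protocol*

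**What the plan says.** **Stopping IP.** Protocol 7.1: "If study intervention is definitively discontinued, the participant will proceed to ET and remain in the study to be evaluated for follow up visits". The local-tolerability paragraph of 7.1 gives the same route: "study treatment will be discontinued permanently, and participant will proceed to ET visit and follow-up". In both Schedules of Activities (1.3.1, 1.3.2) the only column called follow-up is the end-of-study visit, timed at "28–35 Days post-last Dose", so it is anchored to the last dose and not to Day 43. EASI, IGA and BSA, or PASI, PGA and BSA, are scored at ET and at follow-up.

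**Leaving the study.** Protocol 7.2, on the early discontinuation visit: "The participant will be permanently discontinued both from the study intervention and from the study at that time". Section 7.2.1, on participants' own requests: "Participants who request to discontinue receipt of study intervention will remain in the study and must continue to be followed for protocol-specified follow-up procedures".

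**The BSA cap.** Section 6.1.1.1 says that a participant whose treatable BSA passes 20% (AD) or 15% (psoriasis), but not 22% or 16.5%, is retained: "the participant will still remain eligible for the study". Above that: "If the total, treatable BSA exceeds 22% (AD) or 16.5% (psoriasis), the Sponsor may decide to discontinue the participant". Section 8.4 gives the same figures as an exposure limit: "The maximum surface area of administration is 22% BSA for AD and 16.5% for psoriasis participants".

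**Analysis.** SAP 2.1.1 defines the primary estimand (E1) regardless of compliance and treats missing scores as vehicle-like. SAP 6.1.1.1 excludes data only for prohibited medication, and SAP Table 1 records that scores after early drug discontinuation are not censored. SAP Appendix 2.1 sets the Week 6 window at Day 37–57, target Day 43, and keeps the visit closest to the target.

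**The concern.** The analysis is set up to use a Week 6 score from someone who has stopped IP, but the visit schedule does not reliably collect one. Where no score falls in the window, E1 imputes EASI or PASI from the vehicle distribution, and the responder estimand (E2) counts a failure whatever the skin would have shown on Day 43. In many cases a real score could have been had from a participant who was still in the study.

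The BSA-cap sentence adds an ambiguity. Exceeding the cap is in neither the 7.1 list of reasons for stopping IP nor the 7.2 list of reasons for leaving the study, yet 7.1 requires the site to record which of the two has happened. The trigger is also linked to outcome: new disease area feeds EASI and PASI as well as treatable BSA. From the entry maxima of 20% and 15%, just over 2 or 1.5 handprints of new disease (1% of BSA each) cross the cap.

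**Working it through.** The plan states no figure on this point, so there is none to reproduce. The check is day arithmetic.

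**Inputs.** Visit days from the SoA: Week 1 = Day 6–10, Week 2 = Day 13–17, Week 4 = Day 27–31, Week 6 = Day 41–45. Follow-up day = L + 28 to L + 35, where L is the last-dose day: 8 possible days for each of 5 visit days, so 40 combinations. SAP Week 6 window: Day 37–57.

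**Follow-up scores landing in the Week 6 window**

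| Stop at | L = visit day | Follow-up days | In window | In window if L is the day before |
|---|---|---|---|---|
| Week 1 | 6–10 | 34–45 | 5+6+7+8+8 = 34 of 40 | 4+5+6+7+8 = 30 of 40 |
| Week 2 | 13–17 | 41–52 | 40 of 40 | 40 of 40 |
| Week 4 | 27–31 | 55–66 | 3+2+1+0+0 = 6 of 40 | 4+3+2+1+0 = 10 of 40 |

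The Week 4 hits all fall on Day 55–57 (Day 54–57 in the last column), 12–14 (11–14) days after the target. These are counts of allowed calendar days, not probabilities.

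**Stops on any day.** For L = 9 to 22, all 8 follow-up days are in the window. For L = 22 to 30 the number in the window is 57 − (L + 28) + 1 = 30 − L, so it falls from 8 to 0. For L = 30 to 36, follow-up starts at Day 58 or later; if ET is held on the last-dose day it falls in the SAP Week 4 window (Day 26–36), so neither visit supplies a Week 6 score. From Day 37, ET itself is in the Week 6 window. At the other end, L = 1 puts follow-up on Day 29–36, also outside.

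**Study exit.** Nothing is collected after the early discontinuation visit, so a Week 6 score exists only if that visit is on Day 37 or later.

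**If the Week 6 visit were kept.** All 5 allowed days (41–45) are in the window and within 2 days of the target, so the closest-to-target rule selects a score that near Day 43. Time off drug at that visit, against 28–35 days at follow-up:

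- Week 4 stop: 41 − 31 = 10 to 45 − 27 = 18 days
- Week 2 stop: 41 − 17 = 24 to 45 − 13 = 32 days
- Week 1 stop: 41 − 10 = 31 to 45 − 6 = 39 days

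**Weight of one participant in E2.** An active-arm participant who would have responded but is scored a failure moves that arm's rate by 1/28 = 3.6 percentage points (AD) or 1/16 = 6.3 (psoriasis). One who would not have responded moves it by 0. These are the weights of any single participant, with all randomized participants in the mITT set; they do not measure how often the rule bites.

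**The case against.** Several points on the other side are sound.

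- *Follow-up often serves.* After a Week 2 stop it is always in the window, and after a Week 1 stop usually. A reader might infer that everyone who stops IP loses the Week 6 score; the visit windows do not support that. Nor would a kept Week 6 visit bring a Week 1 stopper closer to the last dose (31–39 days off drug against 28–35). The material gain is for stops around Week 4. This stands, and it limits the point.
- *The cap sentence may well mean IP only.* It sits under administration, the cap is an exposure limit in 8.4, and Section 6.4 on non-compliance names the study when withdrawal from it is meant. Against this, the preceding sentence speaks of eligibility for the study. A reader might infer that the cap means study exit; the text does not settle it either way.
- *ET has no fixed day.* One might count every Week 1, 2 and 4 visit day as failing to reach the Week 6 window after study exit, but that only restates the assumption that ET is held on those days. An exit visit from Day 37 counts as Week 6.
- *The plural follow-up visits in 7.1 could include Week 6.* But the local-tolerability text spells out ET and then follow-up, and the SoA labels Week 6 as end of treatment and includes an IP application there. At best this is unclear. Section 7.2.1 does not help: it covers participants' own requests and does not name Week 6.
- *Missing data are already provided for.* The handling is prespecified, and the sample size allows 25% dropout (7 of 28 or 4 of 16 per arm). That is correct, and it is why this is not a conflict with the estimands. It does not explain why an obtainable score is left uncollected.

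**Conclusion.** The point holds, and its main place is Section 7.1: for every definitive IP stop the text provides ET and follow-up but not the scheduled Week 6 visit. The loss is concentrated in stops around Week 4 and up to Day 36, on the assumption that ET is held on the last-dose day. The BSA-cap sentence in 6.1.1.1 is one optional trigger, with the added defect that it does not say what ends; if study participation ends before Day 37, the Week 6 score is lost.

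Two stronger conclusions might be drawn and are not supported. First, that the rule biases the comparison in a known direction: under E1, imputation from vehicle helps the active arm if the lost participant would have scored worse than vehicle and hurts it if better. Second, that the effect on power or on the estimate can be sized: the documents give no rate of crossing the cap or of stopping IP around Week 4, and the Sponsor's decision is discretionary. This is an inexpensive improvement that should be made, not a fault that invalidates the primary analysis.

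**What to change.** **Section 7.1:** state that participants who stop IP for any reason and remain in the study attend the scheduled Week 6 visit (Day 43 ±2) for EASI, IGA and BSA, or PASI, PGA and BSA, in addition to ET and follow-up. Their scores are used as recorded in E1 and E2 unless prohibited medication was started.

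**Section 6.1.1.1:** state that exceeding 22% or 16.5% treatable BSA may lead to discontinuation of IP under 7.1, and is not in itself a reason for withdrawal from the study.

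The SAP windows and the exposure limit stay as they are.

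**Cost.** A short amendment and, for some participants, one more visit of a kind already in the SoA. After a Week 1 or Week 2 stop, follow-up can fall on Day 41–45 in 15 of 40 combinations (last dose on the visit day), so one visit can serve both purposes. A Week 1 stopper whose follow-up would have been on Day 34 might stay up to 45 − 34 = 11 days longer. After a Week 4 stop the Week 6 visit precedes follow-up (Day 55–66), so participation is not extended. The added scores are off treatment. Participants with spreading disease may start prohibited medication before Day 43; their E1 score is then still set to missing and they still count as E2 failures, so not every lost score is recovered. The Sponsor also gives up the option of withdrawing a participant from the study solely for exceeding the cap.
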